**AIM 4 (EFFECTIVENESS)**

In Aim 4, we will involve two groups of participants: (1) parents and their DHH child, and (2) students who will conduct a scoring task

(1) Parents/Caregivers and Children: In Aim 4, parent-child dyads will be recruited from hearing healthcare practices and other organizations that support DHH children and their families in the United States (n=125 dyads). Inclusion criteria: (a) parent is age 18 or older and the custodial guardian; (b) child is aged 3-6 and lives majority of the time in the parent's home; (c) child is DHH and has used a hearing device (HA/CI/bone) for >6 months; and (d) parent can read English, and either speak/understand English or use ASL; and (e) parent lives in a state with an established referral network for parents of DHH children if additional services are needed (e.g. one of the current 39 U.S. states with an authorized chapter of the national Hands & Voices organization). Exclusion criteria: (a) active child protective services case; (b) parent already has accessed behavioral health services for the child; and (c) parent participated in Aim 3.

(2) Up to 200 students will be recruited from the University of Kentucky. Inclusion criteria: (a) current student at the University of Kentucky; (b) native English speaker and (c) age 18 years old or older. Exclusion criteria: (a) ever diagnosed with a hearing loss; (b) more than minimal experience listening to speech produced by deaf or hard of hearing children; and (c) previously participated in this study.

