This pattern will continue (annual assessment for all participants + FCU-DHH sessions for FCU-DHH participants only, follow-up six months later for all participants) up to a maximum of 36 months after baseline, or until the study ends (participants enrolling after the 3/2/2023 IRB modification/approval are anticipated to end participation after the 18-month assessment). All data collection will occur remotely. This includes full (i.e. "annual") parent and child assessments at baseline (including child assessments of speech, language, and hearing for participants enrolled after the 3/2/2023 IRB modification/approval), 12-month, 24-month and 36-month follow-ups for all participants; reduced (i.e., "mid-year") parent-only assessments at 6-month, 18-month, 30-month follow-ups for all participants; and FCU-DHH sessions for only FCU-DHH participants following the baseline, 12-month, and 24-month assessments). All parents/caregivers will be compensated \$75 following the baseline assessments before 3/2/2023 (which do not include child language measures); \$100 for baseline assessments after 3/2/2023 (including child language measures) and each annual assessment, and \$50 for completing each mid-year assessment. With parental permission, each child will be allowed to select a small age-appropriate toy (stuffed animal, book, puzzle, etc.) following their participation in annual assessments to acknowledge their contribution to the study. No compensation will be provided for participation in the FCU-DHH sessions. This strategy is intended to make the intervention itself as similar as possible to what it would be if offered outside of a research protocol. At the completion of the study, Aim 4 parent participants will receive an additional payment of \$100 if all 7 sets of research assessments are completed, an additional \$75 if 6 sets of assessments are completed, an additional \$50 if 5 sets of assessments are completed, and an additional \$25 if 4 sets of assessments are completed. These amounts are intended to compensate parents for their long-term participation and keep parents engaged even if some assessments are missed.

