Description of parent measures: Data collection appointments will be scheduled with each parent-child dyad, on annual and semi-annual basis, as detailed in Form M. All parent/caregiver participants will complete baseline and annual assessments of parent- and child-level constructs, including: a brief sociodemographic background questionnaire also addressing prior healthcare use, child behavior therapy use, and HA/CI adherence (10 minutes); the 100-item CBCL Ages 1.5-5 or the 113-item CBCL Ages 6-18 (15

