At each six-month follow-up assessment (i.e., 6 months, 18 months, 30 months), a subset of these parent measures will be repeated, and the FCU-DHH participants will also complete the Therapy Attitude Inventory (TAI; satisfaction measure; 5 minutes). Parent-report language measures will not be administered at the six-month follow-up assessments to reduce participant burden (i.e., MacArthur-Bates, MAIS). There are also no videotaped FIT tasks at six-month follow-up assessments.

Description of child measures: At annual (12-month, 24-month, 36-month, and baseline for participants recruited after 3/2/2023) assessments, we will administer several key measures of child language development outcomes directly to children: the Ling sounds test (2 minutes); the CELF Preschool-3 (ages 3-6) or the CELF-5 (age 7 years and older; 30 minutes - different subtests used for children 7-8 years vs children 9 years and older); the PPVT-5 (15 minutes); and the BIT (5 minutes). The language assessment will be conducted by Zoom videoconferencing and will be recorded to assist in scoring the assessments per their established protocols. Children will participate in videotaped FIT tasks alongside their parent(s), as described above. Language measures will not be administered at the six-month follow-up assessments (i.e., 6-month, 18-month, 30-month).

Additionally, FCU-DHH participants will complete a 20-item set of questions that assesses their satisfaction with their interventionist (SWI - 5 minutes to complete). Each FCU-DHH participant will answer the SWI questions at the assessment timepoint that most closely aligns with the end of their involvement in the study (e.g., participants who enrolled in 2021 will complete these questions at their 36-month assessment; those who enrolled in 2023 will complete these questions at their 18-month assessment because study funding ends in May 2025). In comparison, the TAI assesses satisfaction with the intervention (not the interventionist) and is repeated at 6-month, 18-month, and 30-month assessments.

For all participants, the battery of measures (see Form M) is written at an 8th-grade reading level or below. Data collectors will be trained by the investigators ([name] for sociodemographic and behavioral measures; [name] for speech and language measures) in standardized protocols for administering these measures.

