Aim 4 data analyses: To make trial arm (FCU-DHH vs. TAU) comparisons, we will utilize linear mixed modeling. In the models, we will utilize random effects corresponding to the interventionists, thus accounting for the possibility of clustering of outcomes from parent-child dyads who received the intervention from the same person. For the analysis of our primary outcome (parenting behaviors as measured by PARYC score at the first 6-month follow-up), a fixed effect for trial arm (FCU-DHH vs. TAU) will be the primary covariate of interest. Additional analyses for Hypotheses 1-4 will address each outcome over time (i.e., PARYC scores as well as continuous measures of child behavior, parent-report and objective adherence with HA/CI, and language development). To account for the correlation among repeated measurements from the same subject, in addition to random effects corresponding to the interventionists, we will also utilize an unstructured within-subject covariance structure. In these multilevel models, trial arm, time (categorical), and their interaction will be used as predictors, with the interaction being of primary interest. All tests will be two-sided with a 5% significance level and will be conducted in SAS Version 9.4 or higher (SAS Institute, Cary, NC). Furthermore, analyses will be based on intention-to-treat.

Principal components analysis and z-scores may be used to create composite language outcomes at each time-point due to the multiple measures proposed, which may reflect a single common trait. 100 Note that because rolling study enrollment is necessary (especially in smaller clinics), some parent-child dyads may have fewer observations than others.

We will measure potentially important predictors (e.g., sex, race, parental age, socioeconomic status, degree of hearing impairment, type of hearing rehabilitation device, baseline language development), and statistically compare the balance of the two trial arms. Secondary analyses will include these variables as covariates within the previously described models.

Prior to analyses, we will inspect variable distributions using histograms, probability plots, and residual plots. If necessary, transformations will be performed to make the variable distributions approximate a normal distribution. Alternatively, generalized estimating equations (GEE) may be utilized.

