## Statistical Analysis Plan

All tests will be two-sided with a 5% significance level and will be conducted in SAS. Analysis methods will account for clustering within parent coaches (i.e., statistical correlation among the outcomes from participants who share the same interventionist). Therefore, analysis of our primary outcome (parenting behaviors as measured by PARYC score at the first 6-month follow-up) will be achieved with linear mixed-effects modeling, with random effects to account for this clustering. A fixed effect for trial arm (FCU-DHH vs. TAU) will be the primary covariate of interest. Additional analyses will address each outcome over time (i.e., PARYC scores, PARCHISY scores, measures of child behavior, parent report and objective adherence with HA/CI, and language development). In longitudinal analyses, linear mixed effects modeling will be adjusted to account for the additional level of correlation among outcomes from the same subject (e.g., a random time effect or an unstructured covariance). Fixed effects will include trial arm, time (categorical or continuous variable), and their interaction, with the interaction being of primary interest. Because rolling study enrollment is necessary, some parent–child dyads may have fewer observations than others. Recommended statistical approaches will be used for missing data within interventionists (e.g., multiple imputation at the subject and cluster level). Sensitivity analyses will be considered and dictated by the type of missing data. We will measure potentially important predictors (e.g., sex, race, parental age, socioeconomic status, degree of hearing loss, type of hearing rehabilitation device, and baseline language development) and statistically compare the balance of the two trial arms. Secondary analyses will include these variables as covariates. Stratified randomization (by device type and poverty level) will be accounted for in analyses.

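### Child age is not named in the main behaviour and language models, which can cost precision and leave chance age imbalance unadjusted, mainly for the directly administered language tests (CELF, PPVT-5, BIT)

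*Combined protocol and SAP*

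**What the plan says.** The Aim 4 inclusion criteria state that the "child is aged 3-6 and lives majority of the time in the parent's home". Follow-up runs "up to a maximum of 36 months after baseline", but families enrolled after the 3/2/2023 modification are expected to finish at the 18-month assessment.

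Two instruments change with the child's age. Parents complete "the 100-item CBCL Ages 1.5-5 or the 113-item CBCL Ages 6-18", and children take "the CELF Preschool-3 (ages 3-6) or the CELF-5 (age 7 years and older", with different CELF-5 subtests from age 9. The directly administered language tests are given at the annual visits, with a "baseline for participants recruited after 3/2/2023" only.

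For the longitudinal outcomes, the protocol (Aim 4 data analyses) says that "trial arm, time (categorical), and their interaction will be used as predictors". The SAP has the same structure: "Fixed effects will include trial arm, time (categorical or continuous variable), and their interaction, with the interaction being of primary interest". Both add coach random effects and within-child correlation, and the SAP also accounts for the strata, device type and poverty level.

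Potentially important predictors are to be compared between arms and then used as covariates in secondary analyses. The protocol's examples are "sex, race, parental age, socioeconomic status, degree of hearing impairment, type of hearing rehabilitation device, baseline language development", and the SAP's list is essentially the same. Parental age is there and child age is not. Child age is among the items requested from medical records. Neither document says whether CBCL, CELF or PPVT-5 scores will be raw or age-normed.

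**The concern.** Time since baseline is not developmental time. At any one visit the children span about four years of age, and raw language scores in this range would be expected to depend on age. A covariate that explains outcome variance and is already on file is left out of the main models. The result is a wider interval for the arm comparison wherever age does not cancel within the child. A chance difference in mean age between 72 and 53 dyads would also stay in the estimate. If scores are raw, children also move between forms of different length or content at different visits, which adds noise to change scores. Hypotheses 2 and 4 are the trial's child-level outcomes, and the sample size was not set for them.

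**Working it through.** **1. The plan's own figure.** The only planned figure is 125 dyads (72 and 53), set for a medium effect on parenting behaviours. Power, SD, intraclass correlation and dropout are not given, so it cannot be reproduced from stated inputs. Assuming d = 0.5, two-sided 5% and 80% power without clustering, equal allocation needs 126 and a 72:53 ratio needs 130. It serves here only as a reference size.

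**2. Which visits each measure has, as planned (annual visits).**

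| Measure | Enrolled before 3/2/2023 | Enrolled after 3/2/2023 |
|---|---|---|
| CELF, PPVT-5, BIT | months 12, 24, 36 | baseline, month 12 |
| SALT, MacArthur-Bates, MAIS, CBCL | baseline, months 12, 24, 36 | baseline, month 12 |

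For the first row, essentially no child has both a direct baseline and a 24- or 36-month score, so comparing those visits means comparing different children. For the second row every family has a baseline.

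**3. Single-visit contrast.** Let R² be the share of outcome variance due to child age (not in the documents; a range is assumed). Take an effect of 0.5 age-adjusted SD and ignore clustering and dropout.

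- √(1/53 + 1/72) = 0.181
- Power without age = Φ(0.5 × √(1 − R²) / 0.181 − 1.96)
- SE ratio, age omitted to age included = 1/√(1 − R²)

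| R² | SE ratio | Power without age |
|---|---|---|
| 0 (same as age in the model) | 1.00 | 79% |
| 0.1 | 1.05 | 75% |
| 0.3 | 1.20 | 64% |
| 0.5 | 1.41 | 50% |

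Fewer than 125 dyads will have scores at months 24 and 36, so absolute power there is lower. The SE ratios do not depend on the number of dyads.

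**4. Chance imbalance in age.** If entry ages are uniform from 3 to under 7 (assumption), the SD is 4/√12 = 1.15 years. The 95% range for the difference in mean age is ±1.96 × 1.15 × 0.181 = ±0.41 years, about 5 months. With an age–score correlation of 0.5 to 0.7 (assumption), this moves an unadjusted single-visit contrast by 1.96 × 0.181 × r = ±0.18 to ±0.25 SD. This is already part of the wider unadjusted SE in step 3, not an extra bias.

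**5. Within-child change contrast.** With a within-child correlation of 0.6 (assumption), the variance of change is 2 × (1 − 0.6) = 0.8, and the SE is √0.8 × 0.181 = 0.16. In simulation (8,000 runs per scenario, 72 against 53) the SE was 0.16 with or without age when age shifted only the level. When growth also differed by 0.2 SD per year of entry age, it was 0.167 without age and 0.162 with it. A form offset affecting a share p of children adds p(1 − p) × offset² to the variance of change. For p from 0.25 to 0.75, an offset of 0.5 SD raises the SE by about 3–4%, and 1 SD by about 11–15%.

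Simulated type I error was 4.6–5.8% without age and 4.6–5.5% with it.

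**6. How many children change form (uniform entry ages).**

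- CBCL, baseline to month 12: entry age 5 to under 6, or 1/4 = 25%.
- CBCL, baseline to month 36, among those followed that long: entry age 3 to under 6, or 3/4 = 75%.
- CELF, first given at month 12 and followed to month 36: under 7 at month 12 (entry below 6) and at least 7 at month 36 (entry 4 or above), so 2/4 = 50%.

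**The case against.** The strongest defence has five parts.

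- **The predictor list is illustrative.** Both versions are introduced as examples, so a reader who infers that child age is excluded goes too far. It is simply not committed to, and listed variables reach only secondary analyses.
- **The planned contrast is arm by time.** Categorical time absorbs average growth, and stable age differences largely cancel within the child. This stands for SALT, MacArthur-Bates, MAIS and CBCL. A reader might infer that no language measure has a baseline for early families, but the protocol collects these at baseline for everyone. The defence fails for CELF, PPVT-5 and BIT, because of the visit pattern in step 2. The SAP also allows continuous time, and neither coding absorbs age-dependent growth or form changes.
- **Scores may be age-normed.** CBCL percentiles are already used for safety referral, and the language tests follow their established scoring protocols. That makes normed scores likely, but does not fix the efficacy metric. The optional z-scores are described by time-point, not by age.
- **Randomisation protects validity.** It does. Inflated type I error or systematic bias is a tempting inference that neither the design nor the simulation supports.
- **Larger figures do not carry over.** Correlations of 0.5 to 0.7 give 1/(1 − r²) − 1 = 33% to 96% more dyads, but only for raw single-visit scores, not for Hypotheses 2 and 4 in general. Similarly, 25% and 75% are the shares on CELF-5 at months 12 and 36, not the shares observed to change version.

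**Conclusion.** The point holds as one of precision and of unadjusted chance imbalance, concentrated in CELF, PPVT-5 and BIT under Hypothesis 4. On a raw single-visit contrast, omitting age lowers power from 79% to between 75% and 50% for age shares of 10% to 50%. These shares, the 0.5 SD effect and the uniform entry ages are assumptions. With fully age-normed scores the loss is near zero. For outcomes with a baseline in every family, what remains is age-dependent growth and any form offset: small unless the offset approaches 1 SD.

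The form changes do not affect the primary outcome, PARYC at 6 months. The missing statement on raw or normed scores is, taken alone, a gap in detail. It matters here because it decides how large the loss is.

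**What to change.** In the Aim 4 data analyses and the SAP:

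1. Add child age at baseline as a fixed effect in the main Hypothesis 2 and Hypothesis 4 models, not only in secondary analyses.
2. Add child age to the variables compared between arms.
3. State that age-normed scores will be used where the CBCL or CELF form changes with age, so that scores from different forms share one scale.

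An indicator for the form used is optional, as a sensitivity analysis. The cost is SAP wording and one extra fixed-effect term; child age is already collected. The change should be fixed before outcome data are examined by arm.

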#### AIM 5 (IMPLEMENTATION)

In Aim 5, implementation outcomes and factors associated with implementation will be assessed with parent coaches and key stakeholders using quantitative and qualitative methods. Stakeholders identified through our professional networks will complete key informant interviews and quantitative measures with a trained interviewer. Additionally, we will purposively select a subsample of parents with varying outcomes and characteristics who received the FCU-DHH to participate in post-intervention key informant interviews. The semi-structured key informant interviews will seek constructive feedback regarding successes and obstacles to the intervention delivery. Quantitative measures will assess characteristics of the interventionists as well as stakeholders' perceptions of the FCU-DHH.

(1) Procedures for Interventionists ("parent coaches"): In Aim 5, following the informed consent procedure, parent coaches (n=10) will complete training involving: 1) online training to deliver the Family Check-Up (FCU) program (approximately 20-25 hours over multiple days; conducted by an FCU trainer); 2) human subjects protection training using the CIRTification curriculum (as described in Aim 3) (approximately 4 hours); and 3) online training covering adaptations specific to the FCU-DHH program (approximately 5 hours); and 4) additional logistics training (e.g., home visiting safety, mental health "red flags" (See Section 10), data management systems, and reviewing human subjects protection training (approximately 8 hours). Coaches who received the previous phases of training prior to the COVID-19 shutdowns will be re-consented and will be required to complete virtual refresher training courses on all components of training (approximately 12 hours over four days). Parent coaches will be included in the IRB's Study Personnel List. Upon completion of all training activities, the parent coaches will complete a post-training baseline assessment (see Form M and description below).

Adapted FCU-DHH intervention delivery materials will be used for intervention delivery. Parent coaches will receive clinical supervision from a clinical supervisor trained in the FCU (currently [name], a clinical psychologist listed as study personnel through the University of Colorado, a relying IRB site), between all meetings with parents/caregivers. They will also attend bimonthly group supervision meetings with other parent coaches and the clinical supervisor. (Note that any clinical supervisor on the study is also trained in human subjects protection and included in study personnel because they will be interacting with the parent coaches who are research participants and viewing videos of parent/child dyads.) [name], who is a licensed clinical social worker, will also be available for back-up supervision and consultation via cell phone. During the phase of intervention delivery, parent coaches will complete monthly online process logs detailing time, attendance, supervision contacts, additional contacts with families, and other expenses associated with intervention delivery. They will also complete fidelity checklists at each appointment with a family. Additionally, one FCU-DHH session per interventionist per year will be video-recorded (with permission from all parties) and coded for fidelity using the COACH rating system created by the original developers of the FCU. Each parent coach will deliver the FCU-DHH to approximately 5-10 families per year.

Following training (or retraining), coaches will complete a battery of measures assessing interventionist-level implementation science constructs. Two weeks after the completion of the final FCU-DHH session with their final families, parent coaches will complete post-intervention assessments (see Form M and description below). Measures used have demonstrated reliability and validity in measuring interventionist and intervention constructs important in implementation science. The research staff will also conduct an audio-recorded,

semi-structured key informant interview with each parent coach aimed at obtaining feedback regarding their experiences with the FCU-DHH and any successes and obstacles to the FCU-DHH intervention delivery.

All training and intervention delivery activities will be paid at an hourly wage. Parent coaches will be mailed checks for \$25 at baseline for completing the set of questionnaires which will take about 20 minutes, and they will receive \$50 at post-test for completing the final set of questionnaires and the interview, which will take approximately 60 minutes.

Description of parent coach measures: Post-training baseline assessments include sociodemographic background questionnaire assessing sociodemographic characteristics and any work experiences with children/families and/or mental health training/practice; the 15-item EBPAS, assessing attitudes toward evidence-based practice; the 41-item CASES, assessing self-efficacy to deliver the intervention; the 20-item PCIS, assessing perceived characteristics of the intervention; and the 14-item TPA, assessing the acceptability of training and the intervention. Post-intervention quantitative assessments will include the EBPAS, CASES, and PCIS assessments, as well as the 16-item TSI. These are all established quantitative measures in implementation research.

(2) Procedures for Key Stakeholders: At the end of intervention delivery, administrators of the Hands & Voices program or other organizations that support DHH children and/or their families, hearing healthcare providers/administrators, and state-level administrators will complete post-test assessments and will be interviewed by a trained interviewer. Measures administered to administrators will include instruments with demonstrated reliability and validity in measuring contextual constructs important in implementation science. Research staff will also conduct an audio- or video-recorded (per the participant's preference), semi-structured key informant interview with each stakeholder, aimed at obtaining constructive feedback regarding experiences with the FCU-DHH delivery, including successes and obstacles. Administrators will be compensated \$50 at post-test for completing the battery of assessments, which will take approximately 90 minutes.

Description of key stakeholder measures: Research staff will conduct an audio-recorded, semi-structured key informant interview with each stakeholder, aimed at obtaining constructive feedback regarding experiences with the FCU-DHH delivery, including successes and obstacles. Key stakeholders will complete a sociodemographic background questionnaire assessing sociodemographic characteristics and level of engagement/awareness with the FCU-DHH intervention. They will also complete the 12-item AIM/IAM/FIM, assessing acceptability, appropriateness, and feasibility of the intervention. These are all established quantitative measures in implementation research.

(3) Procedures for parents: Research staff will conduct an audio-recorded, semi-structured key informant interview with each parent enrolled in Aim 5, aimed at obtaining constructive feedback regarding experiences with receiving the FCU-DHH. Parents who complete key informant interviews will receive \$25 (in addition to compensation received in Aim 4).

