**AIM 5 (IMPLEMENTATION)**

In Aim 5, we will involve three groups of participants: (1) interventionists ("parent coaches"), (2) key stakeholders, and (3) parents who received the FCU-DHH intervention.

(1) Interventionists ("parent coaches"): In Aim 5, parent coaches (n=10) will be enrolled as study participants. Additional coaches will be enrolled if previously enrolled coaches withdraw from the study. Inclusion criteria: 1) age 18 years or older, and 2) willing to complete the FCU-DHH training curriculum, deliver FCU-DHH, and provide interventionist-level data. Exclusion criteria: none

(2) Key Stakeholders: During Aim 5, we will identify key stakeholders (n=10), including hearing healthcare providers, clinic and state administrators, and representatives of the non-profit organization Hands & Voices or other organizations that support DHH children and/or their families. Inclusion criterion: the participant must be in one of the above categories. Exclusion criteria: None.

(3) Parents: In Aim 5, we will purposively select parents with varying outcomes and characteristics (n=20) who received the FCU-DHH to participate in post-intervention key informant interviews.

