#### Data Analyses

For Aim 5, the convergent mixed-methods design will allow simultaneous consideration of quantitative and qualitative data from multiple perspectives to contextualize and gain a more complete understanding of key implementation factors linked with the effectiveness and implementation outcomes of the FCU-DHH. Because this is a type I hybrid trial with a relatively small sample of interventionists and stakeholders, Aim 5 data analyses are primarily descriptive and intended to inform future implementation and scale-up of the FCU-DHH in hearing healthcare settings. Qualitative data analyses will be conducted as described under Aim 2. For quantitative measures of implementation outcomes and factors, descriptive statistics will summarize data within and across the hearing healthcare practices assigned to the intervention condition. If analyses in Aim 4 detect between-coach differences in effectiveness outcomes within the FCU-DHH group, differences in coach-specific implementation outcomes and factors will be examined to identify possible patterns contributing to differential effectiveness. Exploratory analyses targeting implementation outcomes and factors will be conducted between the FCU-DHH clinics regardless of effectiveness outcomes, using models appropriate for the small sample size and levels of data. Qualitative analyses of key informant interviews will be conducted as described in Aim 2.

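### The coach post-test and interview are triggered by finishing the final families, with no provision for coaches who leave, so these parts of Aim 5 risk describing only coaches who stayed

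*Combined protocol and SAP*

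**What the plan says.** The protocol's Study Population section for Aim 5 states that "parent coaches (n=10) will be enrolled as study participants" and continues: "Additional coaches will be enrolled if previously enrolled coaches withdraw from the study". It gives no expected number of withdrawals and no cap on replacements.

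The Research Procedures section for Aim 5 (Interventionists) collects coach data at three stages:

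- **After training.** "Following training (or retraining), coaches will complete a battery of measures assessing interventionist-level implementation science constructs". The instruments are a background questionnaire, EBPAS, CASES, PCIS and TPA.
- **During delivery.** Coaches submit monthly process logs and a fidelity checklist for each family appointment. One recorded session per coach per year is rated with COACH.
- **At the end.** "Two weeks after the completion of the final FCU-DHH session with their final families, parent coaches will complete post-intervention assessments". On content: "Post-intervention quantitative assessments will include the EBPAS, CASES, and PCIS assessments, as well as the 16-item TSI". The section also plans a "semi-structured key informant interview with each parent coach aimed at obtaining feedback". The $50 payment is made "at post-test for completing the final set of questionnaires and the interview", which puts the interview at the same time point as the questionnaires.

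The Data Analyses section for Aim 5 calls the work mainly descriptive. It adds that, if Aim 4 finds effectiveness differing between coaches, "differences in coach-specific implementation outcomes and factors will be examined to identify possible patterns contributing to differential effectiveness".

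Neither the protocol nor the SAP describes an assessment or interview for a coach who stops early, or says how a withdrawn coach's data are reported.

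**The concern.** The Objectives section gives Aim 5 the task of finding what influences implementation, including characteristics of the interventionists, and of reporting outcomes such as acceptability and adoption. A coach who stops delivering is direct evidence on that question. The coach interview is the planned source for coaches' own accounts of what went well and what got in the way, yet its trigger is an event that an early leaver may never reach.

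Two things are at stake. First, post-test scores and interview themes could describe only those for whom the role was workable, and they are meant to inform scale-up. Second, the coach-by-coach comparison could lack post-intervention data for just those coaches whose results need explaining. Parents are treated differently: interviewees are chosen for varied outcomes, and Aim 4 dropouts are compared with those who remain. Coaches have no equivalent.

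**Working it through.** The plan gives no figure to reproduce, so the check sets the sections side by side and adds one illustrative calculation.

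**Step 1. Which coach data depend on finishing?**

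| Component | When collected | Depends on finishing the final families? |
|---|---|---|
| Background, EBPAS, CASES, PCIS, TPA | After training | No |
| Process logs | Monthly during delivery | No |
| Fidelity checklists | Each appointment | No |
| COACH-rated session | One per coach per year | No |
| EBPAS, CASES, PCIS (repeat) | Post-test | Yes |
| TSI | Post-test only | Yes |
| Coach interview | Post-test | Yes |

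Pre-post change in EBPAS, CASES and PCIS needs both rows, so it also depends on finishing. The TPA, the coach measure described as assessing acceptability, is taken after training only and is not exposed to attrition during delivery.

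**Step 2. Can other records replace the interview?** Process logs cover time, attendance, supervision and other contacts, and expenses. The attachment list describes the supervisor log as a monthly time log. Neither is described as recording why a coach left.

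**Step 3. How many coaches could be missing?** The planned number is 10 (Study Population, Aim 5). Let w be the number of withdrawals, each followed by one new enrolment, and suppose all ten coaches in place at the end complete the post-test. Ever-enrolled coaches then number 10 + w, and the share without post-test data is w/(10 + w):

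- w = 1: 1/11 = 9%
- w = 2: 2/12 = 17%
- w = 4: 4/14 = 29%

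The documents do not give w, so these values are assumptions. With w = 0 there is no gap.

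**Step 4. Does the gap reach the coach comparison?** Aim 4 is analysed by intention to treat, and both the protocol's Aim 4 data analyses and the SAP model clustering by interventionist. Families served by a coach who later left therefore stay in the analysis, while that coach has no post-intervention scores or interview. This requires that the coach delivered to at least one family before leaving. A coach who left during training would have none.

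**The case against.** A reader might infer that all of Aim 5's coach-level findings come only from coaches who stayed. The documents do not support that. As Step 1 shows, coach characteristics, baseline self-efficacy and perceived intervention characteristics, training acceptability, fidelity and time data are collected before or during delivery. Nothing says they are discarded when a coach withdraws, so leavers and stayers can be compared on them.

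A reader might also infer that acceptability is overstated. The coach measure of it precedes delivery, and parents (TAI) and stakeholders (AIM/IAM/FIM) supply other acceptability data. Nor do barriers go wholly unrecorded: administrators of the partner organisation, whose executive director supervises the coaches, are among the stakeholders to be interviewed about obstacles. That is a second-hand account, and it does not replace the coach's own.

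It is tempting to attach a size to the bias. If leavers rated one point lower, the mean would be too high by the shares in Step 3, about 0.17 points for two leavers and 0.29 for four. The documents give neither that gap nor reasons for leaving, so even the direction is an assumption.

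Two further objections have force. The trigger refers to each coach's own final families, and the interview is planned with each coach, so the text does not exclude assessing someone who stops early. Form M, cited for the schedule, is an attachment that could not be checked. But no procedure in the available text provides for such an assessment. Also, replacement follows withdrawal from the study, and a person who has withdrawn research consent cannot simply be assessed. That limits the remedy and is respected below.

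**Conclusion.** The point holds for three components: the post-intervention battery, the pre-post change derived from it, and the coach interview. Followed as written, the plan gives a coach who leaves mid-delivery no described route to any of them. The coach comparison would lack the same data for a departed coach whose families remain in Aim 4.

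The possible gap is 9% to 29% of ever-enrolled coaches for one to four withdrawals, on the assumption that each is replaced and all final coaches complete the post-test. With about ten coaches, one or two missing accounts could change a descriptive or qualitative conclusion. Whether scores are too high, too low or unaffected cannot be determined.

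The consequence is limited. Aim 5 is mainly descriptive, the coach comparison is conditional on a finding in Aim 4, and the Aim 4 primary outcome does not use these measures. This is an inexpensive improvement and does not threaten the trial's main result.

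**What to change.** - Change the trigger in the Aim 5 procedures so that the existing post-intervention battery and interview are offered, voluntarily, to each consented coach when that coach's delivery ends for any reason. Include coaches who have already stopped and agree to be contacted. Exclude those who withdrew consent for research.
- Report the numbers of coaches enrolled, withdrawn and assessed beside every post-intervention result.
- State that departed coaches' earlier data stay in the coach comparison.
- Describe leavers separately where the small number allows confidentiality to be kept.

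The cost is a short modification using instruments already in place and about $50 per additional coach. Some leavers will decline.

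Timing may limit what can be done. The protocol expected funding to end in May 2025 and the project to end on 8/31/2025. The most recent modification, with files dated September 2025, concerns stakeholder interviews, so the documents do not show whether coach data collection is still open. If it has closed, the denominators and the limitation can still be reported at no cost.
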